2.7.2.1.1 Data Handling

Adverse events will be coded using the Medical Dictionary for Regulatory Activities (MedDRA) version 21.0 and assessed according to the Common Terminology Criteria for Adverse Events (CTCAE) version 4.03, respectively.

The CTCAE represents a comprehensive grading system for reporting the acute and late effects of cancer treatments. CTCAE grading is by defining a 5-point scale generally corresponding to mild, moderate, severe, life threatening, and death. This grading system inherently places a value on the importance of an event, although there is not necessarily proportionality among grades (a Grade 2 is not necessarily twice as bad as a Grade 1).

If CTCAE grading does not exist for an AE, Grades 1, 2, 3, or 4 corresponding to the severity of mild, moderate, severe, and life-threatening, respectively, will be used. CTCAE Grade 5 (death) will not be used in this study. Death information will be collected on the “Death” eCRF pages.

2.7.2.1.2 Data Analysis

AE Summaries

AE summaries will include all AEs occurring during on-treatment period, i.e. treatment emergent AEs. Treatment emergent AEs (TEAEs) include all AEs that started on or after the first administration day of study treatment and up to last study administration day of study treatment +30 days. All AEs collected in the AE (e)CRF page will be listed along with the information collected on those AEs, eg, AE relationship to study drug, AE outcome, etc. Treatment-emergent AEs will be flagged in the listings.

TEAEs will be summarized by number and percentage of subjects having at least one TEAE, having at least one TEAE in each primary system organ class (SOC) and for each preferred term (PT) using MedDRA coding. A subject with multiple occurrences of an AE will be counted only once in the respective AE category. A subject with multiple CTCAE grades for the same preferred term will be summarized under the maximum CTCAE grade recorded for the event. AE with missing CTCAE grade will be included in the 'All grades' column of the summary tables.

In TEAE summaries the primary system organ class will be presented alphabetically, and the preferred terms will be sorted within primary SOC in descending frequency. The sort order for the preferred term will be based on their frequency in FAS. The following TEAE summaries will be produced by treatment and by FGFR2 fusion/translocation status:

- Overview of TEAEs and deaths (number and % of subjects who died from fatal TEAE, number and % of subjects with any TEAE, any treatment emergent serious AE, any TEAE leading to dose reductions/interruptions, TEAE leading to discontinuation of study treatment)
- All TEAEs by SOC and PT and worst grade
- Treatment related TEAEs by SOC and PT and worst grade
- Grade 3 or 4 TEAEs by SOC and PT and worst grade
- Treatment emergent serious AEs (SAEs) by SOC and PT and worst grade
- Treatment emergent serious treatment-related AEs by SOC and PT and worst grade
- TEAE with fatal outcome by SOC and PT and worst grade
- TEAE leading to study treatment discontinuation by SOC, PT and grade
- TEAE leading to dose interruption/adjustment by SOC, PT and grade
- TEAE leading to treatment discontinuation by SOC and PT and worst grade
- TEAE requiring additional medication or therapies by SOC and PT and worst grade
- All TEAEs by PT by descending order of frequency
- Treatment related TEAEs by PT by descending order of frequency
- All TEAEs occurred in $\geq 10\%$ subjects by PT by descending order of frequency
- Grade 3 or 4 TEAEs by PT by descending order of frequency
- Treatment related Grade 3 or 4 TEAEs by PT by descending order of frequency
- Treatment emergent serious AEs (SAEs) by PT by descending order of frequency
- Treatment emergent serious treatment-related AEs by PT by descending order of frequency
- TEAE leading to treatment discontinuation by PT by descending order of frequency
- TEAE requiring additional medication or therapies by descending order of frequency

The following listings will be produced:

- All adverse events
- All serious adverse events

Deaths

Primary reason for on-treatment, post-treatment and all deaths will be summarized for the full analysis set. Treatment-emergent AE with fatal outcome will be summarized by SOC and PT. On-treatment death will also be summarized by SOC and PT.

All deaths will be listed and on-treatment death will be flagged.

Adverse Events of Special Interest

Adverse events of special interest (AESI) will be considered. Each AESI consists of one or more well-defined safety events which are similar in nature and for which there is a specific clinical interest in connection with the study treatment(s) (Section 5.2 to Section 5.8). For each specified AESI, number and percentage of patients with at least one event within the AESI will be reported. The following AESI will be considered for this study:

- Calcium phosphate homeostasis, including the subcategories of hypercalcemia, hyperphosphatemia, and hypophosphatemia
- Eye disorder
- Central Serious Retinopathy/Retinal Pigment Epithelium Detachment (CSR/RPED)
- Cardiac disorder
- Acute pancreatitis
- Tissue calcification
- Pathological fracture
- Vascular calcification/mineralization

For each AESI (or its subcategory), the overall summary of the characteristics will be provided. In addition, each AESI will also be summarized by subcategory (as applicable), preferred term and worst grade. The current search strategy for each AESI is documented in Section 5.2.

Minimum Critical Toxicities

Minimal critical toxicities are toxicities that should always be explicitly considered during the planning for the development of every new medicinal product (Section 5.9). Analyses of these are based on FDA guidance as applicable (ie, Drug Induced Liver Injury using Hy's Law per FDA guidance).

Minimal critical toxicities to be analyzed under this statistical analysis plan include the following categories:

- Cardiac toxicity including QT prolongation and other ECG abnormalities
- Hepatotoxicity
- Nephrotoxicity
- Hematologic toxicity

Subject incidence of TEAEs indicative of potential cases of the toxicities will be summarized for each of the categories.

For hepatotoxicity, in addition, abnormalities in liver function tests will be summarized. Subject incidence of the following will be provided:

- $3\times$ -, $5\times$ -, $10\times$ -, and $20\times$ upper limit of normal (ULN) elevations of aspartate aminotransferase (AST) and/or alanine aminotransferase (ALT).
- Any elevations of bilirubin; elevated total bilirubin to $\geq 2\times$ ULN.
- Any elevations of alkaline phosphatase (ALP) $>1.5\times$ ULN.
- Elevation of “ALT or AST” ($>3\times$ ULN) accompanied by elevated total bilirubin ($>1.5\times$ ULN, $\geq 2\times$ ULN) and ALP $<2\times$ ULN.

In addition, a listing of potential Hy’s Law cases identified will be provided. Potential hepatotoxicity is identified by the Hy’s Law (FDA Guidance for Industry Drug Induced Liver Injury: Pre-marketing Clinical Evaluation, July 2009) as: ALT or AST $>3.0\times$ ULN; total bilirubin $\geq 2.0\times$ ULN, ALP $<2.0\times$ ULN; and no other confounding factors including preexisting or acute liver disease.

For cardiac toxicity, ECG findings will also be summarized as specified in Section [2.7.3.3](#).

Phosphate Binder Medication

Number of subjects who have taken phosphate binder medication (Section [5.11](#)) and the types of medication will be summarized by the formulation. Of these patients who have taken phosphate binder, number (percentage) of subjects who had a Grade 3/4 hypophosphatemia AE (including preferred terms hypophosphatemia and blood phosphorus decrease) will be summarized.

2.7.2.2 *Laboratory Data*

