#### 8 SAFETY MONITORING AND REPORTING

#### 8.1 Adverse events

## 8.1.1 Definition and reporting

An adverse event is defined as the appearance of (or worsening of any pre-existing) undesirable sign(s), symptom(s), or medical condition(s) that occur after patient's signed informed consent has been obtained. (Adverse events that occur before a patient signs the informed consent are recorded on the Medical History/Current Medical Conditions eCRF.) Adverse events that occur after informed consent is signed and prior to initiation of study treatment will only be captured if they meet the definition of serious adverse events and are reported to be causally related with study procedures (eg, an invasive procedure such as biopsy). All other adverse events occurring after informed consent is signed prior to initiation of study treatment should be recorded as medical history. Adverse event monitoring and recording should be continued for at least 30 days following the last dose of study treatment.

For patients who sign the molecular pre-screening ICF, AEs which occur after signature of this consent will only be captured if they meet the definition of serious as outlined in Section 8.2 and are reported to be causally related with study procedures (e.g. an invasive procedure such as biopsy).

Patients with known FGFR2 gene fusions or other FGFR genetic alteration status will only sign the main study ICF and AE collection for these patients will start from the time of signing the main ICF.

Adverse events (including lab abnormalities that constitute AEs) should be described using a diagnosis whenever possible, rather than individual underlying signs and symptoms. When a clear diagnosis cannot be identified, each sign or symptom should be reported as a separate Adverse Event.

Adverse events will be assessed according to the Common Terminology Criteria for Adverse Events (CTCAE) version 4.03. If CTCAE grading does not exist for an adverse event, the severity of mild, moderate, severe, and life-threatening, corresponding to Grades 1 - 4, will be used. CTCAE Grade 5 (death) will not be used in this study. Rather,

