#### 10.5.2.2 Adverse events (AEs)

Summary tables for adverse events (AEs) have to include only AEs that started or worsened during the on-treatment period, the **treatment-emergent** AEs. However, all safety data (including those from the pre and post-treatment periods) will be listed and treatment-emergent are to be flagged.

The incidence of treatment-emergent adverse events (new or worsening from baseline) will be summarized by system organ class and or preferred term, severity (based on CTCAE grades), type of adverse event, relationship to study treatment.

Deaths reportable as SAEs and non-fatal serious adverse events will be listed by patient and tabulated.

Adverse events of special interest (AESI) will be considered. Each AESI consists of one or more well-defined safety events which are similar in nature and for which there is a specific clinical interest in connection with the study treatment(s).

For each specified AESI, number and percentage of patients with at least one event within the AESI will be reported.

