The overall observation period will be divided into three mutually exclusive segments:

pre-treatment period: from day of subject's first informed consent to the day before first administration of study treatment

on-treatment period: from date of first administration of study treatment to 30 days after date of last actual administration of any study treatment (including start and stop date).

post-treatment period: starting at Day 31 after last administration of study treatment in the single arm.

If dates are incomplete in a way that clear assignment to pre-, on-, post-treatment period cannot be made, then the respective data will be assigned to the on-treatment period.

Safety summaries (tables, figures) include only data from the on-treatment period with the exception of baseline data which will also be summarized where appropriate (eg, change from baseline summaries). In addition, a separate summary for death including on-treatment and post treatment deaths will be provided. Summary tables for adverse events (AEs) will summarize only on-treatment events, with a start date during the on-treatment period (***treatment-emergent AEs***).

2.1.1.6 *Handling of Missing Values/Censoring*

Subjects who are of unknown clinical response or not assessed will be treated as nonresponders in the analyses of overall response rate (ORR).

Subjects who haven't experienced the specified event at the time of analysis will have time-to-event data (eg, progression-free survival, overall survival, etc.) censored at the time of last measurement prior to the data cut-off point used in the report.

2.2 *Analysis Sets*

2.2.1 *Full Analysis Set*

The Full Analysis Set (FAS) includes all subjects who received at least one dose of infigratinib. Unless otherwise specified, all the analyses will be done separately for each cohort.

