4 CHANGE TO PROTOCOL SPECIFIED ANALYSES

None.

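### The SAP's treatment-emergent rule drops the protocol's worsening limb, so an AE or SAE record opened before first dose that worsens on drug can be left out of the TEAE tables

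*SAP*

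**What the plan says.** Protocol 10.5.2.2 requires that AE summary tables "include only AEs that started or worsened during the on-treatment period". Its next paragraph describes the same events as new or worsening from baseline. It also wants safety data from before and after treatment listed, with treatment-emergent events flagged.

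The SAP gives its own definition twice, each time on the start date alone:

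- Section 2.1.1.5: AE tables "will summarize only on-treatment events, with a start date during the on-treatment period".
- Section 2.7.2.1.2: "Treatment emergent AEs (TEAEs) include all AEs that started on or after the first administration day of study treatment", up to 30 days after the last dose. The listing flag for treatment-emergent events follows in the same paragraph.

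The SAP introduction states that it is based on protocol Version 6 (Amendment 5), the version that holds the wider definition. The SAP section headed "CHANGE TO PROTOCOL SPECIFIED ANALYSES" contains only the word None.

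**The concern.** Two current documents define the main safety event differently, and the SAP does not say so. A programmer working from the SAP will build the TEAE flag from the start date. An event whose recorded start precedes first dose, and whose grade rises on drug, is then a TEAE under the protocol and not under the SAP.

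The start-date rule reaches far within the AE outputs. It governs the overall, worst-grade, Grade 3 or 4, serious, treatment-related and fatal TEAE tables in SAP 2.7.2.1.2, and the TEAE subgroup summaries in 2.2.8. It also governs the TEAE incidences for the minimum critical toxicities and, through 2.1.1.5, the tables of events of special interest. Any discrepancy runs one way: the SAP can leave out an event that the protocol counts, never the reverse.

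**Working it through.** The plan states no figure on this point and no arithmetic applies. The check is to trace how a pre-dose event is recorded and then apply each definition to it.

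**How pre-dose events are recorded**

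1. Protocol 8.1.1 includes the worsening of a pre-existing condition in its definition of an adverse event.
2. The same section limits capture between consent and first dose to serious events related to study procedures. Everything else in that interval goes to medical history, as do events before consent.
3. Protocol 7.2.2.1 is broader. Significant physical findings that begin or worsen after consent go on the AE eCRF, with no requirement that they be serious or procedure-related.
4. Protocol 8.2.2 is also broader. Every SAE after consent is reported regardless of causality.
5. Section 8.2.2 treats progression of an SAE as follow-up to the original event, whenever it occurs. It asks for a separate report when an SAE falls in a different time interval or is unrelated. These instructions concern the SAE report; no text says how the matching eCRF record is to be dated.
6. Protocol 8.1.1 collects a severity grade and start and end dates for each AE, and asks that changes in severity be followed. It names no date of grade change. Neither document says that a worsened event takes the date of worsening as its start.

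**Applying the two definitions**

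| Situation | Protocol 10.5.2.2 | SAP 2.1.1.5 and 2.7.2.1.2 |
|---|---|---|
| (a) Condition held as medical history worsens on drug and is entered as a new AE starting on treatment | counted | counted |
| (b) AE or SAE record opened before first dose worsens on drug and keeps its original start date | counted | not counted |
| (c) Event starts on or after first dose, within the on-treatment period | counted | counted |

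The definitions differ only in (b). That class holds chiefly procedure-related SAEs (item 2). It may be wider if sites follow items 3 and 4. It is empty if every worsening is opened as a new record.

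**What still shows a class (b) event**

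SAP 2.7.2.1.2 lists every AE on the eCRF, so the event appears there without the flag. On-treatment deaths are summarised separately in that section, so a fatal outcome is visible even if the fatal-TEAE table omits it. The laboratory worst-grade and shift tables in 2.7.2.2.3 use laboratory values, not AE start dates. Section 2.1.1.5 also assigns data to the on-treatment period when incomplete dates prevent a clear assignment, so class (b) needs a start date that is clearly before first dose.

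**The case against.** The strongest reply is that the recording rules already do the work of the missing limb. Under Protocol 8.1.1 an ordinary pre-dose condition has no AE record. When it worsens on drug, that worsening is an AE in its own right and would naturally start on treatment, where the SAP counts it. This largely stands, and it sets the limit of the point.

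It also disposes of a stronger reading that a reader might infer: that any condition present before dosing which worsens on drug disappears from the AE tables. Inclusion criterion 9 seems to supply examples, since it admits patients with Grade 1 residual toxicity, alopecia or stable neuropathy from prior therapy. The documents do not support that reading. These conditions normally predate consent and are medical history, so their worsening falls in class (a). Nor do the documents support any estimate of patients affected, because they give neither the frequency of class (b) records nor sites' dating practice.

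The reply does not close the gap completely. Sections 7.2.2.1 and 8.2.2 read more widely than 8.1.1 on what is captured before dosing, SAE progression is tied to the original report, and no rule fixes the start date of a worsened event. The protocol itself plans to list pre-treatment safety data and flag the treatment-emergent events, so a rule for records that straddle first dose is needed.

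**Conclusion.** The contradiction between the protocol and the SAP is certain from the text, and SAP Section 4 does not declare it. Its practical effect is narrow: AE or SAE records opened before first dose that worsen on drug and retain their original start date. These are lost from the TEAE tables and the TEAE flag, but not from the all-AE listing. The number is probably small, could be zero, and cannot be derived from the documents. The conclusion rests on two assumptions: that some such records exist, and that at least some sites do not open a new record when the grade rises.

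The point merits correction because the departure is undeclared, can only lower counts and is inexpensive to repair. It concerns an analysis definition, not clinical management. The protocol's inconsistent end of the on-treatment period (90 days in 10.5.2.1, with post-treatment starting at day 31, against 30 days in the SAP) is a separate matter. It does not affect the reasoning here, which turns on the first-dose boundary.

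**What to change.** In SAP 2.1.1.5 and 2.7.2.1.2, define a treatment-emergent AE as one that *started, or worsened in CTCAE grade from the pre-dose grade, during the on-treatment period*. Use the same rule for the flag in the AE listings. Add one sentence stating that a worsening is dated at the grade change.

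If the narrower start-date rule is intended, the alternative is to declare it in SAP Section 4 with the reason.

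The cost is a short amendment to two SAP sections and one derivation. There is a small data cost as well. Protocol 8.1.1 does not name a date of grade change among the items evaluated for each AE, so a few site queries may be needed where that date or the pre-dose grade was not recorded. The queries would be confined to records with a start date before first dose.
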